# 4.7 Conformity of the principles of this study to international, regional, and other standards

This study is conducted in accordance with this protocol, the ethical principles set forth in the Declaration of Helsinki of the World Medical Association (last revision), and the current edition of Good Clinical Practice (ICH GCP E6), the legislation and standards of the Russian Federation: the Constitution of the Russian Federation; the current edition of Federal Law No. 61-FZ of the Russian Federation of April 12, 2010 *On the circulation of medicinal products*; the current edition of Federal Law No. 323-FZ of the Russian Federation of November 21, 2011 *On the basics of protecting the health of citizens in the Russian Federation*; Decree No. 714 of the Government of the Russian Federation of September 13, 2010 *On Approval of Model Rules for Compulsory Life and Health Insurance of a Patient Participating in Clinical Trials of a Medicinal Product*" (as amended on September 4, 2012); Decree No. 393 of the Government of the Russian Federation of May 18, 2011 *On Amendments to the Model Rules for Compulsory* 

CONFIDENTIAL P. 33 of 84

Life and Health Insurance of a Patient Participating in Clinical Trials of a Medicinal Product; Order No. 703n of the Ministry of Health and Social Development of Russia of August 23, 2010 On Approval of the Notification Form for the Completion, Suspension or Termination of a Clinical Trial of a Medicinal Product for Medical Use; Order No. 774n of the Ministry of Health and Social Development of Russia of August 31, 2010 On the Ethics Council, Order No. 200n of the Ministry of Health of Russia of April 1, 2016 On Approval of Good Clinical Practice Guidelines, GOST R52379-2005 Good Clinical Practice and other applicable legislative acts.

#### 5 STUDY GOAL AND OBJECTIVES

### 5.1 Study goal

To evaluate the efficacy, pharmacokinetics, pharmacodynamics, safety and tolerability of RPH-104 following a single injection in adult patients with an acute gout attack.

# 5.2 Study objectives

- To investigate the efficacy of RPH-104 in the treatment of acute gouty arthritis following a single subcutaneous injection at doses of 4, 20, 40, 80 and 160 mg;
- To investigate the pharmacokinetics of RPH-104 following its single subcutaneous injection;
- To investigate the effect of RPH-104 following its single subcutaneous injection on concentrations of high-sensitivity C-reactive protein (hs-CRP), serum amyloid A protein, blood cytokines (IL-1α, IL-1β, IL-1RA, IL-6, IL-8, TNF-α);
- To investigate the safety parameters of RPH-104 in adult patients with an acute gout attack.

#### 6 STUDY DESIGN

# 6.1 Primary and secondary endpoints

#### **6.1.1** Primary efficacy variable

Change in pain intensity in the assessed joint at 72 hours after start of the investigational product therapy compared to baseline, as measured on the visual analogue scale (VAS).

#### **6.1.2** Other efficacy variables

- Change in pain intensity in the assessed joint at 15, 30, 45 minutes, 1, 1.5, 2, 4, 8, 24, 48, 72 hours, on days 5, 6, 10, 15, 18, 22, 29 and 45 after start of the investigational product therapy compared to baseline (as measured on VAS).
- Proportion of patients who rated the response to the investigational product therapy as "Excellent" or "Good" at 15, 30, 45 minutes, 1, 1.5 hours, 2, 4, 8, 24, 48, 72 hours, on days 5, 6, 10 15, 18, 22, 29, and 45 after initiation of the investigational product therapy;
- Change in the degree of swelling, tenderness, erythema in the assessed joint at 24, 48, 72 hours, on days 5, 6, 10, 15, 18, 22, 29 and 45 after start of the investigational product therapy compared to baseline;
- Change in movement restriction in the assessed joint at 24, 48, 72 hours, on days 5, 6, 10, 15, 18, 22, 29 and 45 after start of the investigational product therapy compared to baseline:
- Time to 50% reduction in pain intensity in the assessed joint relative to the baseline level according to the VAS;
- Time to use of the rescue medication;

CONFIDENTIAL P. 34 of 84

- The proportion of patients who received the rescue medication within 72 hours of starting the investigational product therapy and over the entire treatment period;
- Changes in the health assessment questionnaire scores 15, 29, and 45 days after start of the investigational product therapy compared to baseline.

#### **6.1.3** Pharmacokinetic variables

Pharmacokinetic parameters of subcutaneous RPH-104: AUC0-t, AUC0-∞, Cmax, tmax, t1/2, Kel.

#### **6.1.4** Pharmacodynamic variables

- Change in serum hs-CRP levels at 24, 72 hours, 5, 6, 15, 29 and 45 days after start of the investigational product therapy compared to baseline.
- Change in serum amyloid protein A levels at 24, 72 hours, 5, 6, 15, 29 and 45 days after start of the investigational product therapy compared to baseline.
- Change in serum cytokine (IL-1α, IL-1β, IL-1RA, IL-6, IL-8, TNF-α) levels at 24, 72 hours, 5, 6, 15, 29 and 45 days after start of the investigational product therapy compared to baseline.

#### **6.1.5** Safety variables

Frequency and severity of adverse events, laboratory results, vital signs, physical examination findings, ECG findings.

#### **6.1.6** Immunogenicity assessment

Blood samples for immunogenicity assessment will be collected from patients treated with RPH-104 at the following time points: before administration of RPH-104, on Day 15, Day 45. Concentrations of anti-RPH-104 antibodies will be assessed, including an assessment for neutralizing antibodies.

#### 6.2 Study design and study design flowchart

This clinical study is a multicenter, open-label, single-dose, parallel-group, two-period, randomized, phase IIa study to assess the efficacy, pharmacokinetics, pharmacodynamics, safety and tolerability of the investigational product RPH-104.

In study Period 1, eligible patients are enrolled in a group of 22 patients and randomized to receive either RPH-104 4 mg or Voltaren® (diclofenac) in a 15:7 ratio (15 RPH-104 : 7 Voltaren® (diclofenac)). Patients using Voltaren® (diclofenac) will receive the concomitant drug Ortanol® (omeprazole) in order to prevent damage to the gastric or duodenal mucous membrane.

Upon completion of the enrollment of 22 patients, study Period 2 starts. In Period 2, newly enrolled patients are randomly assigned to one of 5 treatment groups: RPH-104 20 mg, 40 mg, 80 mg and 160 mg and active control (Voltaren® (diclofenac)). It is planned to include 14 patients in the RPH-104 groups in Period 2, and 7 patients in the Voltaren® (diclofenac) group.

The enrollment of patients in Period 1 and Period 2 is sequential. There is no pause between the enrollment of patients in Period 1 and Period 2. Thus, patient enrollment for study Period 2 begins immediately after all Period 1 patients are enrolled. Information on the planned total number of patients in the treatment groups is presented in Table 6.1.

CONFIDENTIAL P. 35 of 84

Table 6.1 Number of patients by treatment groups

Treatment group	Study therapy	No. of patients
RPH-104 4 mg	RPH-104, 4 mg, SC, single dose	15
RPH-104 20 mg	RPH-104, 20 mg, SC, single dose	14
RPH-104 40 mg	RPH-104, 40 mg, SC, single dose	14
RPH-104 80 mg	RPH-104, 80 mg, SC, single dose	14
RPH-104 160 mg	RPH-104, 160 mg, SC, divided into 2 injections, 80 mg each at different injection sites	14
Voltaren® (diclofenac)	Voltaren® (diclofenac) 50 mg 3 times a day for 3 days, then 25 mg 3 times a day for 9 days	7 in Period 1 and Period 2 each, total of 14 patients
Total	'	85

Information about the investigational product used for the treatment of acute gout in the patients in this study (RPH-104 or Voltaren® (diclofenac)) and the dose of RPH-104 is unblinded to the patients and physicians. Patients who do not tolerate pain receive the rescue medication after 2 hours and until Day 45 of the study after the first use of rescue medication to intensify therapy. The rescue medication is triamcinolone 40 mg intramuscularly. If an attack recurred after the use of the rescue medication, treatment of acute gout attack is carried out in accordance with the standard practice of the hospital.

[figure not shown]
The primary efficacy variable is assessed 72 hours after initiation of the investigational product use. Secondary efficacy variables are evaluated over a 45 day period of therapy and follow-up.

[figure not shown]
The safety of the investigational product is assessed over a 60-day period of therapy and follow-up.

The study flow diagram is shown in Figure 6.1. The total duration of the study for one patient does not exceed 70 days.

RPH-104 4 mg once: n=15

CONFIDENTIAL P. 36 of 84

\* Screening procedures must be performed within 24 hours and the patient is randomized during this time. If necessary (in exceptional cases), the screening period can be extended, while randomization must be carried out no later than 120 hours (5 days) after the onset of an attack.

Figure 6.1 Flow diagram of the study design.

# 6.3 Subjectivity minimization measures

#### 6.3.1 Randomization

In Period 1, eligible patients are randomized to receive either RPH-104 4 mg or Voltaren® (diclofenac) in a 15:7 ration, i.e. 15 RPH-104 : 7 Voltaren® (diclofenac)).

In Period 2, eligible patients are randomized to receive either RPH-104 20 mg, 40 mg, 80 mg and 160 mg or Voltaren® (diclofenac) in a 2:2:2:2:1 ratio, respectively.

A summary of the treatment groups and the number of patients per group is provided in Table 6.1.

The randomization will be carried out on the basis of a pre-generated randomization list with a random sequence of randomization of patients generated by the software.

CONFIDENTIAL P. 37 of 84

The patient will be randomized by assigning the patient a number and a short name of the therapy group, for example, RPH-104 4 mg. An Interactive Web Response System (IWRS) with technical support service will be used to randomize the patient. Randomization is carried out by the investigator Information about the patient group assigned at randomization is to be recorded in the source documentation.

#### 6.3.2 Blinding

This is an open-label study. Information about the drug for the treatment of acute gout attacks is unblinded to patients and investigators. In this study, there are subjective criteria for assessing the efficacy of study therapy, and information about the drug taken may affect the evaluation of the efficacy of the investigational product by the investigator and the patient. However, since this study is exploratory and is conducted with the aim of assessing the possibility of treating patients with an acute gout attack with RPH-104 in principle, the open-label design of the study is considered acceptable. The efficacy data from this study are not intended to be used to determine the sample size in blind studies.

#### 7 SELECTION OF THE PATIENT POPULATION

In this study, up to 135 adult patients with an acute gout attack will sign the main informed consent form and undergo screening procedures.

At screening, it is planned to select 85 patients meeting all the eligibility criteria for the study described in this section for further participation in the study and initiation of treatment with the investigational product.

# 7.1 Principal diagnosis

Adult patients with an acute gout attack are eligible for the study.

#### 7.2 Inclusion criteria

To initiate treatment of patients with the investigational product and to carry out the investigation procedures specified by the protocol after the screening visit, patients had to meet all the inclusion criteria:

- 1. The patient gave his / her informed consent to participation in this study; the Informed Consent Form was signed both by the patient and the Investigator;
- 2. Male and female patients aged 18 to 80 years inclusive;
- 3. Established diagnosis of gout according to the criteria established by the American College of Rheumatology (ACR) and European League against Rheumatism (EULAR) in 2015;
- 4. Pain in at least one joint at the screening and immediately prior to initiation of therapy with the investigational products, with intensity of 50 mm to 100 mm on the Visual Analogue Scale (VAS);
- 5. Development of acute gout attack within 120 hours (5 days) prior to the randomization date;
- 6. A history of 1 or more acute gout attacks prior to the Screening Visit;
- 7. Patients receiving uric acid-lowering agents had to continue receiving these drugs at a stable dose for at least 4 weeks prior to enrolment to the study and throughout the study; the patients not receiving uric acid-lowering drugs might start receiving this treatment after the end of the study;
- 8. Body mass index  $\leq 40 \text{ kg/m}^2$ ;
- 9. QTcF interval  $\leq 450$  msec for menand  $\leq 470$  msec for women on ECG at screening;
- 10. For women with childbearing potential: negative serum pregnancy test at screening;

CONFIDENTIAL P. 38 of 84

- 11. Consent of women of childbearing potential and men who have female partners of childbearing potential to abstain from sexual intercourse or to use effective methods of contraception throughout the study and for 60 days after RPH-104 administration (if the patient receives RPH-104), as described in Section 9.9;
- 12. The patient's ability to fulfil the requirements of the Study Protocol, as judged by the Investigator.

#### 7.3 Exclusion criteria

Patients are not eligible for the study after the screening period if they meet any of the following criteria:

- 1. The patient received therapy with ibuprofen at a dose of up to 400 mg inclusive within 4 hours or >400 mg within 8 hours prior to the randomization;
- 2. The patient received therapy with diclofenac at a dose of up to 50 mg inclusive within 8 hours or >50 mg within 24 hours prior to the randomization;
- 3. The patient received any other non-steroidal anti-inflammatory drug (NSAID) within 24 hours prior to the randomization;
- 4. The patient received opioids within 48 hours prior to the randomization;
- 5. The patient received metamizole or metamizole-containing drugs within 12 hours prior to the randomization;
- 6. The patient received any analgesic drug (including paracetamol) within 6 hours prior to the randomization;
- 7. The patient received a long-acting NSAID (half-life ≥24 hours) within 5 half-life periods or 1 month prior to the randomization, whichever is longer;
- 8. The patient received naproxen, meloxicam, nabumetone, celecoxib, etoricoxib or extended-release indomethacin within 5 days prior to the randomization;
- 9. The patient received corticosteroids (including intra-articular and inhaled) within 4 weeks prior to the randomization;
- 10. The patient received colchicine within 7 days prior to the randomization;
- 11. Intolerance of or contraindications to NSAIDs;
- 12. Contraindications to Ortanol® capsules 20 mg;
- 13. Chronic heart failure, NYHA functional class II-IV;
- 14. A history of or current clinically significant ventricular arrhythmias or clinically significant atrial tachyarrhythmias;
- 15. Unstable angina or stable exercise-induced angina, functional class III or IV;
- 16. Secondary gout, chemotherapy-induced gout, lead- or transplantation-induced gout;
- 17. Rheumatoid arthritis, confirmed or suspected infectious septic arthritis or any other type of acute inflammatory arthritis;
- 18. Clinically significant renal impairment determined based on creatinine clearance (estimated using the Cockcroft-Gault formula) <60 mL/min, or patients on hemodialysis;
- 19. Blood coagulation disorders; a history of gastrointestinal bleedings or perforation;
- 20. Pregnant or breast-feeding women;

CONFIDENTIAL P. 39 of 84

- 21. Elective surgery or major surgical intervention (minor surgical procedures, such as catheter placement or bone marrow biopsy, are not exclusion criteria) within 14 days before the first dose of the investigational medicinal product;
- 22. Current or suspected HIV-infection, HBsAg, Hepatitis C Virus antibodies (HCVAb), other acute or chronic bacterial, fungal or viral infections at the time of enrolment to the study;
- 23. Presence of any risk factors for tuberculosis based on the results of assessment using the Tuberculosis Risk Assessment Questionnaire at the screening or confirmed tuberculosis or any other infectious disease of the lungs or bronchi based on chest X-ray (2 views) findings performed within 3 months prior to the screening visit, or the need for anti-TB medications, such as isoniazid during the study;
- 24. Neutropenia, leukopenia, or thrombocytopenia determined based on the following laboratory parameters assessed at screening:
  - a. Absolute neutrophil count (ANC) below  $1.5 \times 10^9$ /L;
  - 6. White blood cell count below  $4.0 \times 10^9/L$ ;
  - B. Platelet count below  $150 \times 10^9/L$ ;
- 25. Immunization with live vaccines within 3 months prior to the subject's enrolment to the study or planned vaccination within 60 days after the expected date of the first dose of the investigational product;
- 26. A history of allergic reactions to biological drugs, Voltaren® (diclofenac) or Ortanol® (omeprazole);
- 27. Contraindications to subcutaneous, intramuscular, intravenous or intra-articular injections;
- 28. A history of malignancy (except for patients with localized *in situ* basal cell carcinoma of the skin or *in situ* cervical cancer, who could be enrolled to the study immediately after the treatment for this disease), unless it is in remission for ≥5 years, as well as patients who are investigated for cancer or patients with a suspected malignancy;
- 29. A condition or disease, which, in the Investigator's opinion, could jeopardize the patient's safety or affect the investigational product safety assessment;
- 30. Any other conditions and diseases, such as uncontrolled diabetes mellitus, uncontrolled hypertension, congestive heart failure, exacerbation of peptic ulcer disease, clinically significant liver diseases, kidney diseases, uncontrolled thyroid dysfunction, unhealed wounds, ulcers or bone fractures, psychiatric disorders, uncontrolled epilepsy, drug dependence, which could prevent the patient from complying with this Study Protocol;
- 31. Use of biologicals or investigational medicinal products within 5 half-life periods of these drugs or 3 month prior to the randomization, whichever is longer;
- 32. Blood donation or blood loss of  $\geq$ 400 mL within 8 weeks prior to the randomization.
- 33. The patient was already randomized in this clinical study.

# 8 WITHDRAWAL FROM THE STUDY AND PREMATURE TERMINATION OF THE STUDY

If a decision has been made to withdraw a patient early from the study following the study drug administration, the investigator must schedule a follow-up visit for the patient within 7 days, if possible. If this is not possible, the patient must be invited for a follow-up visit as soon as possible in the period exceeding 7 days. At this visit, it is necessary to carry out all the assessments specified for this visit (see Section 10.3).

CONFIDENTIAL P. 40 of 84

If a patient is excluded from the study due to an AE or a laboratory abnormality, the patient must be monitored until the AE resolved or his/her condition stabilized.

# 8.1 Early withdrawal from the study

The withdrawal criteria are:

- Withdrawal of informed consent.
- Patient's death.
- Patient's pregnancy.
- A significant protocol deviation, which, in the opinion of the Investigator, and upon agreement with the Sponsor, could result in an incorrect interpretation of the study results.

The use of a rescue medication, prohibited drugs, and missing certain procedures or individual visits are generally not the reasons for discontinuation of the patient from the study. In these cases, the patient should be offered to continue the visits and examinations in accordance with the clinical study protocol.

The Investigator should make all reasonable efforts to determine the reason of the patient's withdrawal from the study. The date and reason for the patient's early withdrawal from the study had to be clearly described in the CRF for any patient who received at least one dose of the investigational product.

If a patient is withdrawn from the study due to pregnancy, the Investigator provides the Sponsor with information concerning the pregnancy outcome (see Section 12.7).

Regardless of the reasons for early withdrawal from the study, no replacement of withdrawn patients is to be made.

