## 11.1.6 Diagnosis of infections (HIV, hepatitis B, hepatitis C)

On Day 1, prior to patient randomization, the investigator will look for symptoms and signs of hepatitis B and C, including a medical history data. If a patient is suspected of having hepatitis B or C, the patient is not randomized.

To diagnose infections (HIV, HBsAg, HCV Ab) in patients, blood samples are taken on Day 1 prior to randomization for the following tests:

- Express tests for the diagnosis of HIV (OraQuick HIV ½), hepatitis B (SD BIOLINE HBsAg) and hepatitis C (OraQuick HCV Ab)
- Tests for HIV, HBsAg, HCV Ab performed at the central laboratory

Rapid tests for the study are provided by the sponsor. The Sponsor may provide analogs of the above rapid tests for the study. Details on how to perform rapid tests and how to handle blood samples to diagnose infections at the central laboratory are provided in the laboratory manual.

CONFIDENTIAL P. 60 of 84

All rapid tests must be negative to randomize patients into the study.

Central laboratory testing for HIV, HBsAg, and HCV Ab is performed for all patients who signed the informed consent, regardless of rapid test results. The results of these tests will be known after administration of the investigational product to the patient(s) or a decision has been made to not to include the patient from the study. If the patient's test result at the central laboratory is positive for an infection, it will be communicated to the patient. Such patients will be referred to a specialist for further examination and treatment. For such patients, information about the identified concomitant infectious disease should be entered in the eCRF in the Concomitant Diseases section.

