#### 13.1.6 Missing data

Efficacy data

All efficacy data recorded for a patient after the use of the rescue medication or a prohibited drug with an analgesic effect by the patient will be considered missing.

The baseline observation carried forward method (BOCF) will be used to impute missing data for the main efficacy analysis. This method assumes that missing patient data will be replaced with a baseline value from the time patients withdraws from the study or the rescue medication use is started.

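### Dosed patients can be withdrawn for an undefined significant deviation by an investigator who knows the arm; before 72 hours this sets the primary endpoint to zero change

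*Combined protocol and SAP*

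**What the plan says.** Protocol section 8.1 gives four grounds for early withdrawal: withdrawn consent, death, pregnancy, and a deviation thought to threaten how the findings are read: "A significant protocol deviation, which, in the opinion of the Investigator, and upon agreement with the Sponsor, could result in an incorrect interpretation". Neither that section nor any other defines significant. The same section adds that rescue medication, prohibited drugs and missed procedures or visits are generally not grounds, and that patients in those situations should be offered continued visits. Withdrawn patients are not replaced.

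The criterion reaches treated patients. Section 8 opens with the words "If a decision has been made to withdraw a patient early from the study following the study drug administration" and then requires one follow-up visit, within 7 days if possible. Section 10.3 lists its minimum content: adverse events, concomitant therapy, vital signs, physical examination, weight, ECG and laboratory tests, plus PK and anti-drug antibody samples for patients given RPH-104. No pain VAS or other efficacy item is listed.

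On knowledge of the arm, section 6.3.2 states: "Information about the drug for the treatment of acute gout attacks is unblinded to patients and investigators". The sponsor is not named there, and no sponsor blinding is described anywhere.

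On missing data, section 13.1.6 states: "The baseline observation carried forward method (BOCF) will be used to impute missing data for the main efficacy analysis". It explains that "missing patient data will be replaced with a baseline value from the time patients withdraws from the study" or from the start of rescue. Under section 13.1.1 a randomised, dosed patient needs only one VAS score after the start of therapy to be in the efficacy population. Section 11.4.1 schedules the first at 15 minutes.

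Section 9.7 adds a second discretionary route, in the diclofenac arm only. If a patient took less than 80% of the prescribed dose, the investigator and sponsor discuss possible discontinuation from the study.

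**The concern.** Whether a deviation distorts interpretation is a question for the analysis, where it can be answered with the data kept. Section 8.1 answers it by stopping data collection, on a judgement made while the arm is known and pain scores are accumulating. Section 6.3.2 itself accepts that knowing the drug may affect how efficacy is evaluated.

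RPH-104 is given once (section 9.5.3), so withdrawal after dosing stops no further RPH-104. It stops scheduled observation. Combined with section 13.1.6, it can also replace a real pain response with zero. At stake are the 72-hour comparison in small groups and the later VAS, PK and antibody data after an exposure with a half-life of about 10 days (section 4.3.2).

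**Working it through.** **1. The plan's own precision figures.** Section 13.1.2 gives an SD of 26 mm, 14 per group (15 at 4 mg), an interval accuracy of 30 mm, and significance for pairwise differences of 20 mm or more.

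- Full width of the 95% interval: 2 × t(0.975, 13 df) × 26/√14 = 2 × 15.01 = 30.02 mm.
- Smallest observed difference that reaches two-sided 5%: critical value × 26 × √(2/14) = 19.26 mm (normal), 19.56 mm (t, 79 df) or 20.20 mm (t, 26 df).

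Both figures reproduce, so 20 mm is a fair yardstick.

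**2. What withdrawal does to the primary endpoint.**

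- Withdrawn before 72 h: the score becomes baseline, change = 0, and the patient remains in the efficacy population.
- Withdrawn after 72 h: imputation starts later, and the primary value stays as observed.

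**3. Size with 14 per group.** If k patients with true fall c are set to zero, the group mean moves toward zero by k × c/14. The documents give neither k nor c, so both are assumed. Baseline pain of 50 to 100 mm (section 7.2) caps c at 100 mm.

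| True fall c (mm) | k = 1 | k = 2 |
|---|---|---|
| 25 | 25/14 = 1.8 mm | 3.6 mm |
| 40 | 40/14 = 2.9 mm | 5.7 mm |
| 50 | 50/14 = 3.6 mm | 7.1 mm |
| 70 | 70/14 = 5.0 mm | 10.0 mm |
| 100 | 100/14 = 7.1 mm | 14.3 mm |

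Against 20 mm, one patient is 9% to 36% and two are 18% to 71%. These are shifts in the raw mean; the ANCOVA-adjusted mean will differ somewhat. The withdrawn patient's own arm looks less effective, so the direction of bias in a comparison depends on the arm.

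**4. Size in the 47-patient analysis (section 13.7).** Assume Period 1 was filled (15 on 4 mg and 7 on diclofenac, 22 in all) and that Period 2 ran to its 2:2:2:2:1 ratio. Then 47 − 22 = 25 patients are in Period 2. For one patient with c = 40 mm:

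- each 20 to 160 mg arm: 25 × 2/9 = 5.6 patients, 40/5.56 = 7.2 mm;
- diclofenac: 7 + 25/9 = 9.8 patients, 40/9.8 = 4.1 mm;
- 4 mg: 15 patients, 40/15 = 2.7 mm.

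**5. What else stops.** After withdrawal before 72 h, a follow-up visit within the 7-day target falls no later than 3 + 7 = 10 days after dosing. That is about one half-life, and before the Day 15 and Day 45 antibody samples in section 6.1.6. Terminal half-life and AUC to infinity may then not be estimable, which could cost the patient a place in the PK population (section 13.1.1).

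**6. The compliance route.** The diclofenac course is 3 × 3 + 9 × 3 = 36 tablets, and 80% is 28.8. The documents do not say when compliance is computed. If it is over the whole course, the decision falls after 72 h and touches only later assessments. The route has no counterpart in the RPH-104 arms.

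**The case against.** The strongest reply is that the rule is narrow and its consequences limited. Section 8.1 already keeps patients after rescue, prohibited drugs and missed visits, which covers many likely deviations. Dosed patients stay in the safety population, and those with one VAS score after dosing stay in the efficacy population. To alter the primary endpoint, a deviation must be found, judged significant, agreed with the sponsor and acted on within three days of dosing. The study is exploratory, acknowledges its open-label limits, plans no formal hypothesis testing (section 13.7) and leaves analysis detail to a separate plan. All this stands and limits the point. It does not remove it: other deviations are unprotected, and the planned group means and confidence intervals shift whether or not a test is performed.

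Some stronger inferences are not supported:

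- **That late infection results will trigger these withdrawals.** Sections 11.1.6 and 11.1.7 say results arrive after dosing or after a decision not to include the patient. For positives they prescribe notification, referral and recording; neither mentions withdrawal.
- **That withdrawal ends all follow-up.** One safety, PK and antibody visit remains (sections 8 and 10.3), and adverse events are followed until resolved or stable (section 12.9).
- **That investigator and sponsor both certainly know the arm and the scores.** Only patients and physicians or investigators are named. Sponsor knowledge of the arm is a reasonable inference from the open-label design and from the discussions in section 9.7. Nothing says the sponsor sees VAS scores when agreeing.
- **That 7.2 mm applies to any group at the interim.** It applies only to the 20 to 160 mg arms.

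**Conclusion.** The point holds in a limited form. Section 8.1 permits an undefined, discretionary withdrawal of dosed patients by an investigator who knows the arm. Section 13.1.6 then converts withdrawal before 72 h into zero change at the primary time point. Scheduled VAS and later PK and antibody sampling stop whenever the withdrawal occurs.

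One such patient moves a full-size group by an assumed 1.8 to 7.1 mm. In the 47-patient analysis an assumed 40 mm fall gives about 7.2 mm in a 20 to 160 mg arm. The count and the size of the fall are assumptions, as are a filled Period 1 and allocation to ratio. The documents do not show that any such withdrawal occurred or is likely. The change is still worth making: the rule followed as written can bias the primary result, the groups are small, and section 4 says the interim report may become final.

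**What to change.** 1. In section 8.1, remove protocol deviation as a reason for withdrawing a dosed patient from the study. Treatment decisions are separate and stay with the clinical team.
2. Align section 9.7 so that the under-80% diclofenac compliance discussion does not end study assessments.
3. Keep these patients in all scheduled visits and analyse their observed scores, subject to the existing rule in section 13.1.6 for rescue and prohibited analgesics.
4. In the statistical analysis plan due before interim data lock (section 13.1.7), define important deviations and classify them without reference to arm or VAS. Show the 72-hour endpoint without those patients only as a sensitivity analysis.

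The cost is protocol wording and one table, with no visits beyond those already scheduled. Items 1 to 3 change data collection only for patients recruited later. The 47 interim patients have completed participation, so for them only the analysis part applies: item 4 and the use of any observed scores already on record.
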